8.1.3 Assessment of Adverse Events by the Investigator

The severity of all AEs should be graded according to the CTCAE version 5.0. For those AE terms not listed in the CTCAE, the following grading system should be used:

Assessment of severity

The severity of all AEs should be graded according to the CTCAE version 5.0. For those AE terms not listed in the CTCAE, the following grading system should be used:

- CTCAE Grade 1: Mild; asymptomatic or mild symptoms; clinical or diagnostic observations only; intervention not indicated;
- CTCAE Grade 2: Moderate; minimal local or noninvasive intervention indicated; limiting age-appropriate instrumental activities of daily living;
- CTCAE Grade 3: Severe or medically significant but not immediately life-threatening; hospitalization or prolongation of hospitalization indicated; disabling; limiting self-care activities of daily living;
- CTCAE Grade 4: Life-threatening consequences; urgent intervention indicated; or
- CTCAE Grade 5: Death related to the AE.

Assessment of causality

The relationship of an AE to the administration of the study drug is to be assessed according to the following definitions:

No (unrelated, not related, unlikely to be related) – The time course between the administration of study drug and the occurrence or worsening of the AE rules out a causal relationship and another cause (concomitant drugs, therapies, complications, etc) is suspected.

Yes (possibly, probably, or definitely related) – The time course between the administration of study drug and the occurrence or worsening of the AE is consistent with a causal relationship and no other cause (concomitant drugs, therapies, complications, etc) can be identified.

The definition implies a reasonable possibility of a causal relationship between the event and the study drug. This means that there are facts (evidence) or arguments to suggest a causal relationship.

The following factors should also be considered:

- The temporal sequence from study drug administration-
The event should occur after the study drug is given. The length of time from study drug exposure to event should be evaluated in the clinical context of the event.
- Underlying, concomitant, intercurrent diseases-
Each report should be evaluated in the context of the natural history and course of the disease being treated and any other disease the subject may have.
- Concomitant drug-
The other drugs the subject is taking or the treatment the subject receives should be examined to determine whether any of them might be recognized to cause the event in question.
- Known response pattern for this class of study drug-
Clinical and/or preclinical data may indicate whether a particular response is likely to be a class effect.
- Exposure to physical and/or mental stresses-
The exposure to stress might induce adverse changes in the recipient and provide a logical and better explanation for the event.
- The pharmacology and PK of the study drug-
The known pharmacologic properties (absorption, distribution, metabolism, and excretion) of the study drug should be considered.

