4.3.1 Criteria for Potential Interruption or Discontinuation of Study Drug in Individual Subjects

In the event that any of the following criteria are encountered, the Investigator should review the AE with the Medical Monitor as soon as feasible. The Investigator will hold the next infusion pending that review has been completed. The Investigator and Medical Monitor in consultation with the Sponsor will decide whether to continue to hold study treatment pending additional information or to discontinue study treatment.

- \geq Grade 3 AE or clinically significant laboratory abnormality per Common Terminology Criteria for AEs (CTCAE) version 5.0 considered attributable to AP-SA02 (confirmed by unblinding). If the event or laboratory test is not listed in the CTCAE, the event or laboratory test should be graded by applying the CTCAE guidelines detailed in [Section 8.1.3](#); or

Note: Clinically significant laboratory abnormalities classified per above should be confirmed with a repeat test within 24 hours.

- Clinical signs or symptoms of severe allergic or anaphylactic reaction.
- Any SAE considered to be at least possibly related to AP-SA02 (confirmed by unblinding).

Any subject who prematurely discontinues from study drug should continue to be followed per protocol for safety and key efficacy endpoints. Study staff should make every effort to complete the full panel of assessments scheduled for Early Termination of Treatment (ETOT). The reason

and date of discontinuation will be documented in the eCRF and the subject should continue to complete all safety assessments at subsequent study visits.

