4.3.2 Criteria for Ad Hoc Data Review Committee Review of Study

In the event that any of the following criteria are encountered, the DRC may, as described in the DRC Charter, convene to review available data and make recommendations, including but not limited to, if the cohort should stop or pause the study, enrollment, or treatment and/or make recommendations to modify the protocol (ie, decrease or change the dose of study drug, modify safety monitoring):

Phase 1b criteria

- If any unacceptable toxicity (as determined by the Investigator or Sponsor's Medical Monitor) occurs;
- If ≥ 1 serious AE (SAE) considered attributable to AP-SA02 (confirmed by unblinding) occurs; or
- If ≥ 2 of all treated subjects experience similar SAEs or Grade 3 (CTCAE version 5.0) AEs meeting the following criteria:
 - Onset between start of dosing and 7 days after last dose; and
 - Considered attributable to AP-SA02 (confirmed by unblinding).

Note: All \geq Grade 3 (CTCAE version 5.0) laboratory abnormalities should be confirmed with a repeat test within 24 hours.

Phase 2a criteria

- If ≥ 1 serious AE (SAE) considered at least possibly attributable to AP-SA02 (confirmed by unblinding) occurs; or
- If ≥ 2 of all treated subjects experience the same or similar adverse events that are Grade 3 or higher meeting the following criteria:
 - Onset between start of dosing and 28 days after last dose; and
 - Considered attributable to AP-SA02 (confirmed by unblinding).

Note: All \geq Grade 3 (CTCAE version 5.0) laboratory abnormalities should be confirmed with a repeat test within 24 hours.

Further enrollment of subjects and dosing of the investigational product should be halted until a safety review of the event is completed. If the DRC recommends, and the Sponsor then implements, stopping study treatment and, subsequently, the Sponsor, independent of or following a DRC recommendation, proposes to restart the study, a substantial amendment will be submitted to regulatory agencies, Institutional Review Board (IRB)/Independent Ethics Committee (IEC), and Office of Human Research Oversight (OHRO). The study will not restart until the amendment has been approved by regulatory agencies and IRB/IECs. These requirements are not applicable if the Sponsor pre-emptively pauses study treatment for subject safety pending DRC review and the DRC recommends resuming study treatments and/or any study modifications recommended do not represent substantial protocol changes.

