8.1.1 Adverse (Drug) Reaction

All noxious and unintended responses to a medicinal product related to any dose should be considered an adverse drug reaction. “Responses” to a medicinal product means that a causal relationship between a medicinal product and an AE is at least a reasonable possibility, ie, the relationship cannot be ruled out.

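### Protocol 8.1.3 has no causality category for an adverse event with compatible timing and an identified alternative cause, and its rule for related events contradicts 8.1.1

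*Protocol*

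**What the plan says.** Protocol 8.1.3 (Assessment of causality) has the investigator judge the relationship to study drug by two definitions. Each joins two conditions with *and*.

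- *No* (unrelated, not related, or unlikely related): the time course "rules out a causal relationship and another cause (concomitant drugs, therapies, complications, etc) is suspected".
- *Yes* (possibly, probably or definitely related): the time course "is consistent with a causal relationship and no other cause (concomitant drugs, therapies, complications, etc) can be identified".

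The text then adds: "The definition implies a reasonable possibility of a causal relationship between the event and the study drug". A list of factors to weigh follows, including underlying disease and concomitant drugs. It does not say how to code an event once one of these is recognized as a cause.

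Protocol 8.1.1 defines an adverse drug reaction by a causal relationship that is "at least a reasonable possibility, ie, the relationship cannot be ruled out".

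Relatedness is used in two places that matter here. SAP 3.7.1 gives study drug related TEAEs a row in the adverse event overview and repeats each overview category by system organ class and preferred term. Protocol 4.3.1 and 4.3.2 list criteria for holding study drug and for ad hoc Data Review Committee (DRC) review. Examples are a Phase 2a SAE "considered at least possibly attributable to AP-SA02 (confirmed by unblinding) occurs" and a Phase 1b SAE "considered attributable to AP-SA02 (confirmed by unblinding) occurs". The only pointer from these criteria to 8.1.3 concerns severity: an event that CTCAE does not list is to be "graded by applying the CTCAE guidelines detailed in" that section.

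**The concern.** Finding another possible cause does not exclude the study drug. The *Yes* definition nevertheless makes the absence of any identifiable alternative a condition of being even possibly related, and *No* is open only when timing excludes the drug. An event with compatible timing and an identified alternative is left without a category. The investigator must then pick a box whose definition is not met.

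That situation is easy to reach in this trial. Every subject has *S. aureus* bacteremia and receives BAT, and 8.1.3 itself directs the investigator to look at underlying disease and other drugs. This is also a first-in-human study, and protocol 1.3.2.1 states that no adverse drug reactions have yet been identified. Sites that apply the literal *Yes* rule would code such events as unrelated; sites that follow the reasonable-possibility sentence would code them as related. With approximately 30 to 35 sites planned, the counts of related events could be incomplete and inconsistent between sites.

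**Working it through.** The plan gives no figure to reproduce; the check is one of logic.

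**Step 1. Apply the two definitions to every combination.** Timing has 2 levels (compatible, ruled out) and other cause has 3 (none, suspected only, identified), so there are 2 × 3 = 6 cells.

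| Timing | Other cause | 8.1.3 category |
|---|---|---|
| Compatible | None | *Yes* |
| Compatible | Suspected only | *Yes*, on the most natural reading |
| Compatible | Identified | None |
| Ruled out | None | None |
| Ruled out | Suspected only | *No* |
| Ruled out | Identified | *No* (an identified cause is at least suspected) |

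Totals: *Yes* 2, *No* 2, no category 2. The suspected-only cell is placed under *Yes* because the two definitions use different words: *No* speaks of a cause that is suspected, *Yes* of one that can be identified. Of the two empty cells, the one with timing ruled out has no safety consequence, since the drug is excluded anyway. One safety-relevant cell remains: compatible timing with an identified alternative.

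**Step 2. Compare that cell with 8.1.1.** Timing does not exclude the drug, and an alternative cause does not by itself exclude it. The event can therefore meet the 8.1.1 standard while failing the 8.1.3 *Yes* definition. It also sits badly with two other parts of 8.1.3: the *Yes* label, which includes possibly related, and the sentence on reasonable possibility.

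**Step 3. Count the criteria that use attribution wording.**

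| Section | Criteria listed | At least possibly | Plain attributable |
|---|---|---|---|
| 4.3.1 | 3 | 1 | 1 |
| 4.3.2 Phase 1b | 3 | 0 | 2 |
| 4.3.2 Phase 2a | 2 | 1 | 1 |
| Total | 8 | 2 | 4 |

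So 2 + 4 = 6 of 8 criteria depend on attribution. None of the 8 cites the causality definitions in 8.1.3; 1 of 8 cites 8.1.3, for grading only.

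**Step 4. Check the Phase 1b primary endpoint.** Protocol 7.1 defines it as summaries of TEAEs, vital signs and laboratory evaluations. TEAEs are defined by time of onset, with a longer window for SAEs, and with no relatedness condition. Causality coding does not enter it.

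**The case against.** The strongest reply is that the intended standard can be recovered. The *Yes* label includes possibly related, the next sentence speaks of reasonable possibility, and the listed factors call for clinical weighing. Many investigators would record *Yes* whenever the drug remains plausible. That is fair, but it makes coding depend on which sentence a site follows, and the literal condition still stands.

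Three stronger readings are tempting, and the documents do not support them.

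- *A reader might infer that nearly every event falls into the gap, because BAT and the infection are always present.* Presence makes them candidates; it does not make either the identified cause of a given event. Where an alternative is only suspected, *Yes* remains available.
- *A reader might infer that the Phase 1b primary endpoint is compromised.* It is all-causality, as shown in Step 4. SAP 3.7.1 also tabulates all AEs, TEAEs, SAEs and Grade 3/4/5 events with comparisons of AP-SA02 and placebo; study drug related TEAEs are one of 11 overview rows.
- *A reader might infer that the stopping criteria are disabled.* Section 4.3 does not invoke the 8.1.3 causality definitions, two criteria set their own threshold of at least possibly, and the DRC Charter is not among the documents. An effect is possible but not stated.

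Safeguards that need no attribution also stand: DRC review and ad hoc meetings prompted by trend reviews (3.2), ongoing Medical Monitor review (4.3), discontinuation for any AE regardless of attribution (4.4), and reporting of all SAEs within 24 hours (8.3).

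**Conclusion.** The concern holds as an internal contradiction in a stated rule, and it should be fixed. One of six timing-by-cause combinations is both relevant to safety and without a category, and the *Yes* rule is stricter than the protocol's own standard in 8.1.1.

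The likely consequence is under-attribution at sites that follow the literal wording, so that the overview and by-term tables of study drug related TEAEs may be incomplete. An effect on the 6 of 8 attribution-based criteria in 4.3 is a possibility only. The share of events or triggers missed cannot be derived from the documents; the cell and criterion counts describe wording, not effect.

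The conclusion rests on a literal reading of 8.1.3 and on the assumption that some sites apply it that way. Guidance for completing the eCRF is not in the documents and might reduce the problem.

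**What to change.** Change 8.1.3 only:

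1. Delete the condition in *Yes* that no other cause can be identified.
2. Define *Yes* as a reasonable possibility that the study drug caused or contributed to the event, even if other causes exist, in line with 8.1.1.
3. Define *No* as the complement, no reasonable possibility, and state that unlikely to be related carries that meaning. This also fills the second empty cell.

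Leave the 4.3 thresholds unchanged. Four of the six attribution criteria say plain attributable, and equating that with *Yes* could lower the Phase 1b halt threshold; that is a separate sponsor decision.

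The cost is a wording amendment and matching eCRF completion guidance, with no new data or procedures. The downside is that somewhat more events will be coded related, with possible extra unblinding and DRC reviews. Some temporary halts may follow, since 4.3.2 calls for enrollment and dosing to stop until the safety review of a triggering event is complete.

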8.2 Serious Adverse Events

An AE or adverse reaction is considered serious if, in the view of either the Investigator or Sponsor, it results in any of the following outcomes:

- Death;
- A life-threatening AE;

Note: An AE or adverse reaction is considered “life-threatening” if, in view of either the Investigator or Sponsor, its occurrence places the subject at immediate risk of death. It does not include an event that, had it occurred in a more severe form, might have caused death.

- Requires hospitalization or prolongation of existing hospitalizations;

Note: Any hospital admission with at least 1 overnight stay will be considered an inpatient hospitalization. An emergency room or urgent care visit without hospital admission will not be recorded as an SAE under this criterion, nor will hospitalization for a procedure scheduled or planned before signing of informed consent, or elective treatment of a preexisting condition that did not worsen from baseline. However, unexpected complications and/or prolongation of hospitalization that occur during elective surgery should be recorded as AEs and assessed for seriousness. Admission to the hospital for social or situational reasons (ie, no place to stay, live

too far away to come for hospital visits, respite care) will not be considered inpatient hospitalizations.

- A persistent or significant disability/incapacity or substantial disruption of the ability to conduct normal life functions;
- A congenital anomaly/birth defect; or
- An important medical event.

Note: Important medical events that do not meet any of the above criteria may be considered an SAE when, based upon appropriate medical judgment, they may jeopardize the subject and may require medical or surgical intervention to prevent 1 of the outcomes listed above. Examples of such medical events include allergic bronchospasm requiring intensive treatment in an emergency room or at home, blood dyscrasias or convulsions that do not result in inpatient hospitalizations, or the development of drug dependency.

8.3 Serious Adverse Event Reporting – Procedures for Investigators

Initial reports

All SAEs occurring from the time of informed consent until end of study must be reported to [REDACTED] Clinical Safety within 24 hours of the knowledge of the occurrence.

To report the SAE, complete the SAE form electronically in the EDC system for the study. When the form is completed, [REDACTED] Safety personnel will be notified electronically by the EDC system and will retrieve the form. If the event meets serious criteria and it is not possible to access the EDC system, send an email to [REDACTED] Safety at [REDACTED]

[REDACTED] (contact information listed in [Section 8.6](#)) within 24 hours of awareness. When the EDC system becomes available, the SAE information must be entered within 24 hours of the system becoming available.

Follow-up reports

The Investigator must continue to follow the subject until the SAE has subsided or until the condition becomes chronic in nature, stabilizes (in the case of persistent impairment), or the subject dies.

Within 24 hours of receipt of follow-up information, the Investigator must update the SAE form electronically in the EDC system for the study and submit any supporting documentation (eg, subject discharge summary or autopsy reports) to [REDACTED] Clinical Safety via fax or email. If it is not possible to access the EDC system, refer to the procedures outlined above for initial reporting of SAEs.

8.4 Pregnancy Reporting

If a subject becomes pregnant during the study or within the safety follow-up period defined in the protocol, the Investigator is to stop dosing with study drug immediately and the subject should be withdrawn from the study. ETOT procedures should be implemented at that time.

A pregnancy is not considered to be an AE or SAE; however, it must be reported to [REDACTED] Clinical Safety within 24 hours of knowledge of the event. [REDACTED] Clinical Safety will then

provide the Investigator/site the Exposure In Utero (EIU) form for completion. The Investigator/site must complete the EIU form and fax/email it back to [REDACTED] Clinical Safety.

If the female partner of a male subject becomes pregnant while the subject is receiving study drug or within the safety follow-up period defined in the protocol, the Investigator should notify [REDACTED] Clinical Safety as described above.

The pregnancy should be followed until the outcome of the pregnancy, whenever possible. Once the outcome of the pregnancy is known, the EIU form should be completed and faxed/emailed to [REDACTED] Clinical Safety. If the outcome of the pregnancy meets the criteria for immediate classification as an SAE (ie, postpartum complication, spontaneous abortion, stillbirth, neonatal death, or congenital anomaly), the Investigator should follow the procedures for reporting an SAE.

8.5 Expedited Reporting

The Sponsor/designee will report all relevant information about Suspected Unexpected Serious Adverse Reactions (SUSARs) that are fatal or life-threatening as soon as possible to the FDA, applicable competent authorities in all the Member States concerned, to the Central Ethics Committee, OHRO, and other designated officials as needed (Department of Defense) and in any case no later than 7 days after knowledge by the Sponsor/designee of such a case. Relevant follow-up information will subsequently be communicated within an additional 8 days.

All other SUSARs will be reported to the FDA, applicable competent authorities concerned, and to the Central Ethics Committee concerned as soon as possible but within a maximum of 15 days of first knowledge by the Sponsor/designee.

The Sponsor/designee will also report any additional expedited safety reports required in accordance with the timelines outlined in country-specific legislation.

The Sponsor/designee will also inform all Investigators as required per local regulation.

The requirements above refer to the requirements relating to investigational drug product.

8.6 Special Situation Reports

Special situation reports include reports of overdose, misuse, abuse, medication error, and reports of adverse reactions associated with product complaints.

- **Overdose:** Refers to the administration of a quantity of a medicinal product given per administration or cumulatively (accidentally or intentionally), which is above the maximum recommended dose according to the protocol. Clinical judgment should always be applied. In cases of a discrepancy in the drug accountability, overdose will be established only when it is clear that the subject has taken additional dose(s) or the Investigator has reason to suspect that the subject has taken additional dose(s).
- **Misuse:** Refers to situations where the medicinal product is intentionally and inappropriately used in a way that is not in accordance with the protocol instructions or local prescribing information and may be accompanied by harmful physical and/or psychological effects.
- **Abuse:** Is defined as persistent or sporadic, intentional excessive use of a medicinal product, which is accompanied by harmful physical or psychological effects.

- **Medication error:** Is any unintentional error in the prescribing, dispensing, or administration of a medicinal product by a healthcare professional, patient, or consumer, respectively. The administration or consumption of the unassigned treatment and administration of an expired product are always reportable as medication errors, cases of subjects missing doses of investigational product are not considered reportable as medication error.
- **Product complaint:** Is defined as any written, electronic, or oral communication that alleges deficiencies related to the identity, quality, durability, reliability, safety, effectiveness, or performance of a drug or device after it is released for distribution. A special situations form will only be completed if a complaint is associated with an adverse drug reaction.

